For all secondary outcomes after completing the ITT analysis, we will perform a restricted analysis as described in the additional considerations section above. Specifically, we will restrict the analysis by removing the dyads (patient and family member) based on the T0 transcript of the conversation with the surgeon, which confirms whether the patient discussed surgery with the surgeon and had a vascular or oncologic problem. Next, we will further restrict the analysis based on penetrance of the intervention based on the criteria described above.

Additional important outcomes

Family member presence: We plan to compare the proportion of patients who are accompanied by a family member or “like family” friend to the visit with the surgeon between the intervention and control group as receipt of the QPL prior to a visit with a surgeon may prompt patients to bring a family member with them to the consultation visit for additional decision-making support. This binary outcome variable (yes/no family member present) will be ascertained from the T0 transcript which clearly notes number of family members/friends. Family members do not need to be enrolled in the study to be counted as present. We will use ITT analysis as well as a restricted analysis (as described above) to analyze this outcome.

Consult duration: We will compare the median consult length at T0 between groups. This is not an effectiveness outcome but rather information that clinicians and patients might want to know in considering use of the intervention in their clinic. We will also compare the median consult length within surgeon (pre/post) to account for fairly wide variation in surgeon routine (some surgeons clearly spend

45-60 minutes with patients whereas others spend 7-15 minutes with patients). Given that surgeons will have been assigned randomly to intervention wave the incidence of pre/post measurements will not be evenly distributed and may be too variable to determine real differences.

Exploratory analyses

There are several factors that might impact the effect of the intervention that we have described in our protocol for exploratory heterogeneity of treatment effect (HTE) analysis. These include insurance status (as a marker of socioeconomic status): we will use a binary variable defined by standard insurance (Medicare/private/supplemental) or (Medicaid, dual eligible, charity care, none). We will also consider oncologic indications for surgery as distinct from vascular (as identified in the T0 transcript). We will also consider extent of comorbid illnesses, stratifying patients by Charlson score and categorizing high, medium and low comorbidity.

We will perform additional analysis of OPTION 5 (shared decision making) scores, evaluating the variability in OPTION 5 scores before and after intervention, considering that these scores likely have more between surgeon variability than within surgeon variability. Specifically, we will estimate the correlation on the surgeon random effect pre- and post- intervention.

Aim-3

We will analyze qualitative data with directed content analysis⁴⁵ using a deductive theory-driven analytic framework to evaluate interpersonal and intrapersonal conflict and to compare the similarities and differences between both arms of the study. To enrich the coding process and attend to professional biases, we will include investigators with diverse clinical backgrounds (nursing, palliative care, surgery and patient advocacy). To gain understanding of the trajectory of the patient's story we will triangulate data sources by linking the audio tape of the initial surgeon-patient conversation and the patient's clinical history from chart review, with the follow-up interview. We have previously shown that surgeons see preoperative conversations as a significant event, a time when a two-way agreement is made whereby the surgeon commits to operating and the patient commits to endure potentially burdensome postoperative care.²⁷ We will use this understanding of surgical buy-in to code and analyze preoperative visit and postoperative interview transcripts with the goal of understanding how the contractual relationship that surgeons perceive is experienced by patients. We will explore how postoperative complications were discussed during the initial patient-surgeon interaction with and without the QPL and whether this interaction has impact on subsequent treatment decisions, interpersonal and intrapersonal conflict.

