MYCaW: The difference in the rating of the primary concern between T1 and T2, regardless of the categorization of this concern, as reported by the patient will be treated as a continuous outcome and analyzed with a linear mixed effect model. We will accommodate the longitudinal nature of the data with a patient level random effect. Analyses will be based on a treatment difference relative to T1 at T2 in a random effects model with: a treatment difference at T1, a time (0/1) variable indicating either T1 versus T2, an intervention-by-time interaction representing the treatment difference, and a random effect at the patient level.

We will use linear mixed effects models for continuous responses (MYCaW), logistic random effects models for binary responses (regret).

Further analysis of primary endpoints generated prior to un-blinding

Updated analysis plan and modified power analysis

Rationale: Prior to unblinding (looking at treatment group assignment) and after commencement of data coding in preparation for analysis, the research team became aware of 2 issues that prompted modification

of our per-protocol analysis plan. First, reports from our DSMB demonstrate that PEPPi-5 for this cohort of patients and family members has remarkable ceiling effects (for 333 enrolled participants, mean score 21.4, IQR 20-24, scale range: 0 - 25). Thus, even if we demonstrate a significant difference it would be clinically meaningless. Second, the variability in self-reported concerns using the open-ended MYCaW instrument for patients and family members in this study is enormous. For example, some patients note concerns about parking or how the surgeon communicated with them, whereas others note concerns about removing their cancer or how they will feel after surgery. This makes it difficult to compare concerns between the entirety of the two groups and suggests a need for stratification of these outcomes in relation to the patient's clinical course, specifically whether there was a decision to have surgery. As surgical treatment is a post-randomization variable, such analysis is not appropriate for a primary outcome. In response to these 2 concerns, we recalculated our power analysis without the PEPPi-5 endpoint in aim 1 and without the MYCaW endpoint in aim 2 as these were no longer valid primary outcomes.

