The goal of evaluating MYCaW is to test how much participant-reported concerns change over time for patients who did and did not receive the QPL. Our understanding of the MYCaW measure evolved since the start of the study based on the blinded coding of MYCaW data which revealed a much wider range of problems and concerns in response to MYCaW items than our previous and current review of the literature would suggest. Because not all patients in our study will plan to have surgery after meeting with a surgeon, there is heterogeneity in the description of concerns that is dependent on their treatment plan. Without changing our pre-specified analytic plan, we believe we will have findings that are extremely difficult to interpret. Furthermore, if an effect (positive or negative) of the intervention is identified, it would be challenging to assist surgeons and patients in using these results as many different types of concerns will be lumped together. These proposed changes are responsive to the data and the setting of this trial.

As such, we will conduct a stratified analysis based on the post-randomization variable of a treatment plan to have surgical intervention as determined by the T0 conversation with the surgeon. To this end, our analysis will exclude patients whose treatment plan did not include surgery upon leaving the surgical consultation at T0, and whose treatment plan was unclear at the end of the T0 consultation (this corresponds to categories #2 and #3 below regarding the “treatment plan”).

Within the cohort of patients whose treatment plan includes surgery, we will compare intervention to control patients who noted similar concerns. We will first categorize participants (both patients and family members) by the primary (first) concern expressed and then compare the respondent-reported rating of that concern, assessing the mean score between treatment groups for each category. We will next separate respondents by type: patient and family and repeat this analysis. We will also compare the change of the respondent’s (patient or family member in separate groups) rating of that concern between T1 and T2 using a respondent-level random effects model. We will similarly analyze the change between T1 and T3.

Secondary outcomes: Aim-1: patient engagement [PEPPI-5, OPTION5, HCCQ]

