We selected psychological well-being as an important outcome based on feedback from our patient and family stakeholders who reported significant emotional harm; specifically they felt 'blindsided' when surgical results did not match their expectations. The primary outcome measures to assess psychological well-being are the

Measure Yourself Concerns and Wellbeing (MYCaW) and patient-reported post-treatment regret. MYCaW is a patient-reported outcome measure originally designed for patients with cancer and their family members, which we have adopted for use with patients who have vascular disease. MYCaW allows patients and family members to identify their own most pressing health concerns and rate their well-being. We will administer the MYCaW at the three time points. Patients and family members will report their initial responses to the MYCaW at the time of the first questionnaire, 24–48 hours after the clinic visit. Participants will independently rescore their initial concerns and well-being at the two subsequent time points corresponding to the second and third questionnaires; the difference in scores describes improvement or deterioration in their well-being. To assess treatment-associated regret, we will ask patients and family members at the time of the third and final questionnaire — 'Looking back, is there anything about your treatment/your family member's treatment that you would do differently?' — and transform responses into a dichotomous variable (regret, no regret) for analysis.⁵⁵ We will also analyse these responses qualitatively.

Secondary outcome measures include validated measures from the Patient-Reported Outcomes Measurement Information System (PROMIS) to assess the psychological impact of illness from the patient's perspective.⁵⁶ Patients will receive the Psychosocial Illness Impact-Neg 4a, Psychosocial Illness Impact-Pos 4a and Anxiety 4a; family members will be asked to complete Anxiety 4a and PROMIS short form (SF) Global Health. Because studies of other interventions that support shared decision making show that in some situations informed patients elect more conservative treatment,⁵⁷ we will compare the total number of operations scheduled and performed on enrolled patients by their study surgeon between the control and intervention groups. We will also collect information about potential mediating variables and covariates described in table 3.

Aim 3: postoperative conflict

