In qualitative interviews with a subset of participants who suffered a serious postoperative complication, we will use questions designed to explore the content of patient and family experience with perioperative conflict. The interview guide is structured around open-ended questions about perioperative events, including 'Tell me the story of your experience with surgery'.⁵⁸ The interviewer will follow up the respondents' narrative description with probing on the following domains: patient and family values and goals, decision making, interpersonal relationships (between surgeons and patients/family members, between treating physicians and between family members) and intrapersonal conflict (relating to post-treatment regret and self-blame). We will use feedback during concurrent coding and analysis to prompt additional questioning on emerging themes and trends.

Planned analyses

Quantitative analyses

Our primary analysis will compare the effectiveness of the QPL intervention relative to usual care in regard to patient engagement and patient psychological well-being. We will use an intention-to-treat analysis with all available data from participants based on group assignment. The intervention effect will be tested in the framework of generalised linear mixed-effects models^{59 60} with a treatment dummy variable, surgeon random effect and site-by-time dummy variables to control for site-specific secular trends. We will use linear mixed-effect models for continuous responses such as self-efficacy (PEPPI-5) and well-being (MYCaW), logistic random-effects models for binary responses such as post-treatment regret, and log-linear random-effect models for count-dependent variables such as the number and type of questions asked during the preoperative visit. For linear models, we will adjust for prespecified covariates to increase the statistical precision of our treatment effect estimation.

Our secondary analyses will examine other patient endpoints such as psychological well-being (PROMIS measures) and nature of treatment received. These analyses will also test for intervention effects in family member outcomes such as PEPPI-5, HCCQ, MYCaW, post-treatment regret and psychological well-being. We will use the generalised linear mixed modelling framework used in primary analyses for these outcomes. All models will be estimated and tested using PROC MIXED or PROC NLMIX in SAS V.9.3.

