For each quantitative aim, we desire a family-wise two-sided type I error rate of $\alpha=0.05$; under a Bonferroni correction, tests will be conducted with nominal $\alpha=0.05/2=0.025$ because there are two primary endpoints for aim 1 and aim 2 (table 2). Using patient satisfaction data at one site, we found that between-surgeon variance accounts for only 5% of the total variance. Because power in the stepped wedge design is slightly degraded with greater variance between (vs within) surgeons, we assumed a worst-case scenario between-surgeon variance of 30%. We interpreted this as the interclass correlation between multiple patients of the same surgeon at a given site and included a surgeon-level random effect in our calculation, anticipating between 5% and 30% of the total variance to be accounted for by surgeon effects (ie, interclass correlation (ICC) =0.05–0.30). Extending the information-based method of computing power for a basic stepped wedge design⁴⁹ to the case of our multisite stepped wedge design, we custom-programmed power calculations using R V.3.2.1 (R Foundation for Statistical Computing).

With this method, we computed power of 82% to detect small-to-medium and 93% to detect medium effect sizes of Cohen's $d=0.425$ and $d=0.5$, respectively. Assuming the SD for PEPPI-5 within each treatment arm is 4.3,⁶⁴ we will have 93% power to detect effects as small as 2.15 points. For the number of patient questions, we assumed a mean difference of 1.4 questions between arms.⁴⁰ Assuming overdispersion of two relative to Poisson data, within arm SD=2.7, yielding $d=1.4/2.7=0.52$, which we are well powered to detect. For the MYCaW well-being scale, Jolliffe *et al*⁶⁵ found SD=1.26 at 6 weeks, and a 6-week versus baseline mean difference of 0.59. We will also have 93% power to detect an MYCaW difference as small as $0.5\times1.26=0.63$, comparable with the difference over time in Jolliffe *et al*.⁶⁵ For regret, we assume the upper bound risk of the presence of regret is 0.3,⁵⁵ yielding SD=0.46; we will have over 90% power to detect a regret risk difference of 0.23. Nearly identical power results were obtained via a continuous latent liability model for a binary event (regret).⁶⁶ To account for clustering within sites, this

calculation includes fixed effects terms for site, time (wave) and site-by-time, reflecting our a priori analysis plan.

Qualitative analysis

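### The MYCaW well-being rating is collected but no SAP section analyses it, and the added MYCaW contrasts within concern category are not randomised comparisons

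*Combined protocol and SAP*

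**What the plan says.** **What is collected.** SAP Table 1 lists MYCaW as covering both self-identified concerns and wellbeing, over T1-T2 and T1-T3. The appended published protocol (*Aim 2: psychological well-being*) treats these as two things to be rated: "Participants will independently rescore their initial concerns and well-being at the two subsequent time points".

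**What was sized.** The published protocol's *Quantitative analyses* section assigns a linear mixed model to "well-being (MYCaW), logistic random-effects models for binary responses such as post-treatment regret" (the logistic model in that phrase belongs to regret). Its *Sample size and power calculation* begins the MYCaW statement with "For the MYCaW well-being scale", reports that a cited study "found SD=1.26 at 6 weeks, and a 6-week versus baseline mean difference of 0.59", and concludes "We will also have 93% power to detect an MYCaW difference as small as" 0.5 × 1.26 = 0.63.

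**What the SAP analyses.** Under *Aim-2 primary outcomes [Regret, MYCaW]* the variable is "The difference in the rating of the primary concern between T1 and T2, regardless of the categorization of this concern", as reported by the patient.

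**Why MYCaW lost primary status.** *Updated analysis plan and modified power analysis* says "the variability in self-reported concerns using the open-ended MYCaW instrument for patients and family members in this study is enormous", contrasting parking with cancer removal as examples. It adds that outcomes would need stratifying by clinical course, and that surgical treatment, being post-randomisation, is unsuitable for defining a primary outcome.

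**What was added.** *Stratified Analysis: Aim-2 MYCaW* keeps only patients leaving the T0 visit with a plan for surgery. Within that group "we will compare intervention to control patients who noted similar concerns", by rating of the primary concern in each category and by its change from T1 to T2 and T1 to T3.

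**Other well-being outcomes.** The SAP's secondary Aim 2 section names PROMIS measures only.

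**The concern.** The SAP's stated difficulty is with what participants name: a rating attached to parking cannot sensibly be averaged with one attached to cancer. A well-being rating given by every participant does not carry that difficulty. The reason for demoting MYCaW therefore does not explain why the well-being rating appears in no SAP analysis.

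The added analyses also condition on two things that follow the intervention. The QPL is mailed before the visit. The surgery plan is settled at T0, and the primary concern is recorded at T1, 24-48 hours later. The QPL is meant to change which issues patients raise and may change what they choose. If it moves some patients out of a category or out of the surgery-plan group, those remaining in the two arms differ in kind, and mean ratings can differ even if no individual's rating was altered.

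At stake is a simple randomised comparison on data already in hand, and the risk that category contrasts are read as treatment effects.

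**Working it through.** **1. Reproducing the stated 93%.** Inputs from the published protocol, Table 1 and *Sample size and power calculation*: 40 surgeons, 5 sites, 6 waves, 480 patients, the tabulated crossover schedule, surgeon ICC 0.05-0.30, site-by-wave fixed effects, and two-sided alpha 0.05/2 = 0.025.

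- Patients per surgeon-wave: m = 480/(40 × 6) = 2.
- With total SD 1, a surgeon's six wave means have covariance matrix V, with ρ + (1−ρ)/m on the diagonal and ρ elsewhere.
- Information = Σ X′V⁻¹X over surgeons. X holds the treatment indicator and 30 site-by-wave indicators. SE is the square root of the treatment element of the inverse.
- d = 0.63/1.26 = 0.5. Power = Φ(d/SE − z), with z = 2.241 for alpha 0.025 and 1.960 for alpha 0.05.

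**2. Same calculation at T2.** The SAP gives 222 + 221 = 443 patients and 88% patient completion at T2. 443 × 0.88 = 389.8, about 390, so m = 389.8/240 = 1.624, assuming an even spread over surgeon-waves.

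| ICC | SE, n=480 | Power, 0.025 | SE, n≈390 | Power, 0.025 | Power, 0.05 |
|---|---|---|---|---|---|
| 0.05 | 0.1340 | 93.2% | 0.1469 | 87.7% | 92.6% |
| 0.10 | 0.1368 | 92.1% | 0.1497 | 86.4% | 91.6% |
| 0.15 | 0.1370 | 92.0% | 0.1500 | 86.2% | 91.5% |
| 0.20 | 0.1358 | 92.5% | 0.1488 | 86.8% | 91.9% |
| 0.30 | 0.1305 | 94.4% | 0.1434 | 89.3% | 93.7% |

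Example, ICC 0.30, n≈390, alpha 0.05: 0.5/0.1434 = 3.487; 3.487 − 1.960 = 1.527; Φ(1.527) = 0.937.

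The stated 93% reproduces at its own alpha of 0.025. At T2 the like-for-like figure is 86-89%. The 92-94% applies at alpha 0.05, the more natural level for a secondary outcome outside the primary alpha. At T3 the SAP reports 87% completion (443 × 0.87 ≈ 385), so power is slightly lower.

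**3. Tracing the well-being rating through the SAP.**

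| SAP section | MYCaW score used |
|---|---|
| Table 1 | Concerns and wellbeing listed |
| *Aim-2 primary outcomes* | First-concern rating, T1 to T2, all patients |
| *Updated analysis plan* | MYCaW dropped as primary |
| *Stratified Analysis: Aim-2 MYCaW* | First-concern rating, surgery-planners, by category |
| *Secondary outcomes: Aim-2* | None (PROMIS only) |

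The rating is listed once and analysed nowhere.

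**4. What cannot be sized.** The documents give no SD for the concern rating, no share of patients planning surgery and no number or size of concern categories. A detectable difference within category, or the size of a selection effect, would rest wholly on invented inputs, so none is given. That selection is possible follows from the order of events alone.

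**The case against.** **The power statement is ambiguous.** The published protocol pairs constructs with instruments, so its well-being wording may simply mean MYCaW as a whole. It also says that the difference in scores, for concerns and well-being together, describes change in well-being. Which score the SD of 1.26 describes rests on a cited study not available here. This stands. A reader might infer that the trial was sized on the well-being item and that the SAP switched to another score; the documents do not establish that. On either reading the item is collected and not analysed.

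**PROMIS covers the construct.** Illness impact and anxiety for patients, and global health and anxiety for family members, are analysed at T2 and T3, by intention to treat first. This also stands. A reader might infer that Aim 2 has lost its all-patient well-being comparison; it has not.

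**The all-patient concern analysis may survive.** It remains in the SAP text, and the update calls itself additional. The stratified section does speak of changing the plan, so its status is unclear, but nothing cancels it explicitly.

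**A common item is not trouble-free.** T2 falls 1-2 weeks after surgery, or 6-8 weeks after the visit without surgery, so well-being will reflect clinical course. True, but the same holds for PROMIS, which the SAP analyses. An unrestricted comparison by assignment still avoids selecting on post-intervention variables.

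**The SAP acknowledges the post-randomisation problem.** It does so for the surgery plan, but gives no such caution for the named concern. The T1-T2 and T1-T3 change models do not remove the difficulty: they use the same selected groups, and T1 itself follows the intervention.

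**Conclusion.** The point holds in a limited form. One collected item, the MYCaW well-being rating, has no analysis in the SAP, and the reason given for demoting MYCaW does not apply to it as far as concern content goes. Dependence on clinical course remains. The added within-category contrasts are conditioned on two post-intervention variables and should not be read as randomised treatment effects.

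The loss is one secondary comparison. Regret is unaffected as the sole Aim 2 primary outcome under the modified plan, and PROMIS still provides unrestricted well-being comparisons.

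If SD 1.26 applies to the well-being rating, T2 completers supply the item and patients are spread evenly over surgeon-waves, the omitted comparison would have 92-94% power for 0.63 points at two-sided 0.05, and 86-89% at 0.025, over ICC 0.05-0.30. That is enough to make it worth specifying. The size of any selection effect in the category contrasts cannot be estimated from the documents.

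**What to change.** In *Stratified Analysis: Aim-2 MYCaW* and the secondary Aim 2 section:

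- Add, as a secondary outcome, an intention-to-treat comparison of the patient's MYCaW well-being rating at T2 and, separately, at T3. Include all patients, with no restriction by surgery plan or concern. Use the model in *General Analysis Plan* (treatment, surgeon random effect, site-by-time terms). Compare levels, because T1 is not a pre-intervention baseline. Repeat for family members.
- Report the distribution of concern categories by arm.
- Label the within-category contrasts, including the change models, as descriptive.
- State which MYCaW score the published power statement and its SD of 1.26 refer to, and whether the all-patient first-concern analysis is still to be run.

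If the sponsor prefers not to analyse the well-being rating, the SAP should say why.

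The cost is some SAP wording and a few more secondary models, on an item already collected. Primary alpha does not change. More secondary tests add to multiplicity, which reporting should acknowledge.

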The intervention effect will be tested in the framework of generalized linear mixed effects models^{42,43} with a treatment dummy variable, surgeon random effect and site-by-time dummy variables to control site-specific secular trends.

All models will be estimated and tested using SAS version 9.3 (SAS Institute, Cary, NC), specifically PROC MIXED and PROC NLMIX.

We do not plan to impute missing data if the rate of missingness is low. Currently, our rate of missingness is quite low: 97% of patients and 92% of family members have completed T1. For T2, 88% of patients and 86% of family members have completed the survey and for T3 87% of both patients and family members have completed their survey. We plan to exclude variables for which there is no response (rather than impute these variables). Although we have a small number of incomplete audio recordings, we will treat audio recordings where less than half of the encounter with the surgeon was captured (a total of 6 recordings) as completely missing and those with more than half recorded as complete. We will perform sensitivity analysis to test whether this small loss of data impacts our findings by comparing the outcomes with and without inclusion of audio recordings that are more than half complete.

Aim-1 primary outcomes [Question Counting, PEPPi-5]

Aim 1 has five primary outcomes and as such will be analyzed with a Type I error rate of $\alpha=0.01$.

For question counting, we consider four specific types of questions and evaluate them with ordinal categories:

- Number of OPTIONS questions asked by patients and family members (0, 1, 2+)
- Number of EXPECTATION questions asked by patients and family members (0, 1, 2+)
- Number of ADVANCE DIRECTIVES questions asked by patients and family members (0, 1+)
- Number of RISKS questions asked by patients and family members (0, 1, 2+)

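### The listed MYCaW model leaves the tested QPL effect without the surgeon and site-by-wave control the plan promises, and adding those terms as main effects does not restore it

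*Combined protocol and SAP*

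**What the plan says.** **General framework.** The General Analysis Plan tests the intervention effect with a treatment dummy, "surgeon random effect and site-by-time dummy variables to control site-specific secular trends". The Quantitative analyses section of the published protocol (in the Appendix) gives the same framework and names MYCaW among the outcomes it covers. *Time* there means wave: under Sample size and power calculation, the power "calculation includes fixed effects terms for site, time (wave) and site-by-time, reflecting our a priori analysis plan".

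**MYCaW, per-protocol.** Under Aim-2 primary outcomes, the T1-T2 difference in the primary-concern rating, "as reported by the patient will be treated as a continuous outcome and analyzed with a linear mixed effect model". The section then lists the model. It begins with an arm term for T1 and an indicator of questionnaire occasion ("a time (0/1) variable indicating either T1 versus T2"). The effect to be tested and the only random effect come last: "an intervention-by-time interaction representing the treatment difference, and a random effect at the patient level". No surgeon or site-by-wave term is listed, and *time* now means questionnaire occasion.

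**MYCaW, stratified.** Among patients whose plan includes surgery, the SAP will compare the change in "rating of that concern between T1 and T2 using a respondent-level random effects model", and will treat T1-T3 similarly. No fixed effects or surgeon terms are named.

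**Status.** The updated plan, written before unblinding, removes MYCaW as a primary outcome. It restates the surgeon and site-by-time terms for the question types and regret.

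**The concern.** In a stepped wedge, arm and calendar time are confounded by design, because intervention patients come from later waves. The site-by-wave terms break that link. The listed MYCaW model has two records per patient, and its QPL effect is the interaction of arm with T1/T2. A programmer who follows that list, or who adds the general terms to it as main effects, obtains an effect with no adjustment for wave and no allowance for surgeons. Drift over waves in the T1-T2 change would be counted as a QPL effect, and surgeon variation in the change would make the SE too small. Trends and surgeon effects on the rating *level* do no harm, since they difference out.

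Drift in the change is possible. T2 falls 1-2 weeks after surgery for operated patients but 6-8 weeks after the visit for others, so a shift over waves in the operated share or in the wait for surgery would move the change. The published protocol says the timing was chosen to make the schedules similar, and no document reports drift.

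**Working it through.** **Inputs**
- Published protocol, Table 1 and Recruitment: 40 surgeons, five sites, waves 0-5, eight crossing over at each of waves 1-5, two patients per surgeon per wave, 480 patients.
- SAP: 222/221 patients realised; T2 completed by 88% of patients; alpha 0.025 for each Aim 2 outcome (critical value 2.241). Pairs: 443 x 0.88 = about 390.
- Published protocol, Sample size: surgeon share of variance 0.05-0.30; 93% power at d=0.5, 82% at d=0.425.
- Assumed, because no document gives them: drift in the change, and the surgeon share of variance *in the change*.

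**1. The plan's own power.** With site-by-wave dummies and a surgeon random intercept on one record per patient, N=480 and surgeon share 0.05, the generalised least squares (GLS) SE is 0.134 SD. Power at d=0.5 is Phi(0.5/0.134 - 2.241) = 93.2%, and at d=0.425 it is 82.4%. Both match the stated figures. The listed two-record model has SE sqrt(4/480) = 0.0913 SD of change and power of about 99.9%. The stated power therefore belongs to the adjusted one-record model.

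**2. Cancellation.** Write the two-record model with the general terms added as main effects:

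Y(i,t) = a + b·x + c·t + d·x·t + surgeon + site-by-wave + patient + error, with t = 0 at T1 and 1 at T2.

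Within a patient, Y(i,1) - Y(i,0) = c + d·x + error difference. The surgeon, site-by-wave and patient terms drop out, so with complete pairs d is estimated by the raw arm difference in mean change.

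Noise-free check on the Table 1 layout, with drift of 0.10 per wave in the change and no true effect:

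| Model | Estimate of d |
|---|---|
| As listed | 0.233 |
| + surgeon intercept and site-by-wave main effects | 0.233 |
| + site-by-occasion | 0.234 |
| + site-by-wave-by-occasion | 0.000 |
| site-by-occasion + wave-by-occasion | 0.000 |

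With 443 patients and 12% of T2 missing, the first, second and fourth models give 0.237, 0.235 and 0.000.

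**3. Wave gap.** Control surgeons per wave are 40, 32, 24, 16, 8, 0, so the mean control wave is (32+48+48+32)/120 = 1.33. Intervention surgeons are 0, 8, 16, 24, 32, 40, giving (8+32+72+128+200)/120 = 3.67. The gap is 2.33, and bias = 2.33 x drift per wave.

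The realised layout is not given. With 222/221 patients, at most three per surgeon per wave and 56-80 per wave (70-100% of goal), the gap must lie within 1.75-3.17. Random layouts under similar limits gave 2.10-2.59.

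**4. Type I error at 390 pairs.** Nominal SE = sqrt(4/390) = 0.1013 SD. For surgeon share s in the change, the true variance is (1-s)·4/390 + s·0.0222.

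| Drift (SD of change per wave) | s = 0 | s = 0.05-0.30 |
|---|---|---|
| 0 | 0.025 | 0.029-0.054 |
| 0.01 | 0.029 | 0.033-0.058 |
| 0.02 | 0.041 | 0.046-0.073 |
| 0.05 | 0.14 | 0.15-0.18 |

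Example: drift 0.05 gives bias 0.117 and 0.117/0.1013 = 1.15; the upper tail beyond 2.241 - 1.15 is 0.138. Over the gap range 1.75-3.17 with s = 0, the error is 0.034-0.055 at drift 0.02 and 0.085-0.25 at drift 0.05.

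**5. Smaller subsets.** At drift 0.05 and s = 0, the same formula gives 0.079 at an assumed 200 pairs and 0.051 at 100. The SAP states no alpha for the stratified analysis; 0.025 is carried over here.

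**The case against.** **A reader might infer that the MYCaW section contradicts itself,** since it names a difference score and then lists a two-record model. The text does not support that. A linking sentence says that the longitudinal structure is handled by a patient random effect. Both wordings target the same contrast and, with no other terms, give the same estimate for complete pairs. They part only when the general surgeon and site-by-wave terms are applied. The published protocol's remark that "the difference in scores describes improvement or deterioration in their well-being" does not settle the choice of model either. The conflict is between the general framework and the listed model.

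**The general framework may be meant to fill the gap.** The difference outcome plus the General Analysis Plan already gives the adjusted model, and the power figure agrees. That is a fair account of intent. But the list as written does not produce that model, and neither does the list with the general terms added as main effects.

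**The harm is assumed.** This stands. Drift is not documented, and the 5% surgeon share comes from patient satisfaction data at one site, not from change in MYCaW. With no drift and a 5% share, the error is 0.029 against 0.025.

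**The 390-pair figures do not describe the stratified analysis.** This also stands. Restriction to planned surgery removes most of any shift in operated share, and the subsets are smaller. There, adjustment can cost more than it saves: at drift 0.05 with no surgeon share, unadjusted root mean squared error is sqrt(0.117² + 0.141²) = 0.18 at 200 pairs, against an adjusted SE of about 0.21. At 100 pairs it is 0.23 against 0.33.

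**The 390 pairs ignore T1 non-response.** With T1 at 97% and independent losses, about 378 pairs remain, which changes little.

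**Conclusion.** The point holds as a mismatch between the promised secular-trend control and the listed MYCaW model. The cancellation follows from the model form and needs no assumption about the data. Its practical size depends on an unknown drift: small at 0.02 SD of change per wave or less (type I error about 0.04 or below at 390 pairs without surgeon variation), material from about 0.05 (about 0.14), and smaller in the stratified subsets. These figures assume the planned wave gap of 2.33.

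The documents do not support a reading that drift has occurred, or that the trial's main conclusions are at risk. Only the retained per-protocol and stratified MYCaW analyses are affected.

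**What to change.** **Aim-2 primary outcomes, MYCaW.** State one model:
- the T1-T2 change with treatment, site-by-wave dummies and a surgeon random effect; or
- the two-record model with site-by-wave-by-occasion fixed terms and a surgeon random slope for occasion added.

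The two are equivalent only for complete pairs. The second keeps patients with T1 only, which suits the promise to use all available data.

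**Stratified Analysis.** Apply the same control to the T1-T2 and T1-T3 changes in the whole planned-surgery cohort. Prespecify site plus wave main effects, in the model for the change, for concern categories too small for 30 site-by-wave cells. Report the unadjusted estimate beside the adjusted one, because the precision loss there can exceed the bias removed.

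**Wording.** Use *wave* and *occasion* in place of *time*.

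**Cost.** A few lines of SAP text and code. At 390 pairs the SE rises from 0.101 to 0.143-0.152 SD of change, giving about 85-89% power for 0.63 points (d=0.5) if 1.26 is the SD of the change. The published protocol gives 1.26 only as an SD at 6 weeks. If it is the SD of a single rating, the SD of the change is 1.26 x sqrt(2(1-r)), and power is 70-76%, 85-89% or 98-99% at an assumed T1-T2 correlation r of 0.3, 0.5 or 0.7. The sponsor's own power calculation already carries this loss of precision from wave adjustment.
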